The Stage 1 cross sectional study will investigate two groups of people with dementia aged 60-89 years with 385 people in each group. Group 1 will comprise people living at home and Group 2 will comprise people living in care homes. The sample size has been calculated to allow detection of a prevalence of 50% with 5% precision and 95% confidence based on the reported estimated prevalence of VI in the population (5, 26). Subjects will be recruited through Memory Clinics and Old Age Psychiatry clinics in NHS trusts and through general medical practices with the assistance of DeNDRoN and Local Coordinating Research Networks. Additionally, Group 1 subjects will be recruited through Alzheimers Society local groups and Group 2 subjects will be recruited through direct contact with care homes. Where participants are recruited via AS, they will only be recruited from groups of service users for whom a medical diagnosis of dementia has been confirmed through the AS processes. It should also be noted that recruitment through AS is not intended to be the primary route, but rather an additional source of participants to enhance the overall recruitment strategy. BUPA

has offered to support the study but we will also recruit through other care providers to reduce the risk of selection bias. Further subjects for both groups, especially those living at home, can also be recruited through The Outside Clinic, one of the UK's leading providers of domiciliary eye care services. They have informed us that they test approximately 2,500 people with dementia each year (living in their own homes and in care homes).

Strategy: The team is aware that recruitment of people with dementia into research studies is not easy and we have adopted a multilayered approach to recruitment. It is intended that the majority of subjects for the prevalence study will be recruited with the assistance of regional DeNDRoNs and CLRNs.

DeNDRoN is launching the ENRICH research ready-care home network this year and we will make use of this to recruit participants.

Identification procedures

Potential participants with dementia will be identified from their medical records by the direct care team or by DeNDRoN or Local Coordinating Research staff who are frequently embedded in NHS clinics. In addition DeNDRoN maintain case registers of patients with dementia who are willing to participate in research and suitable participants who are on this register will be identified and approached.

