Stage 2: Data will be collected from focus groups of eye care professionals, family carers and professional (paid) carers and interviews with people with dementia. The focus group question schedule will be semi structured and cover participants' understanding of eye care for people with dementia; expectations of the eye examination; experience of eye examination and eye care of people with dementia; barriers encountered; and facilitators and strategies to improve eye care. Data obtained in each interview will depend on the individual's ability to recall, communicate and comprehend and will vary according to the degree of dementia.

Data analysis

Stage 1 – prevalence, along with their 95% confidence intervals, of VI due to refractive error, cataract, age-related macular degeneration, glaucoma and diabetic retinopathy will be established. These Confidence Intervals will be used to compare the prevalence of the VIs with published figures in the general population. Prevalence levels between people living at home and people living in care homes will be compared using tests for two independent proportions. Proportions of both previously undetected cases and detected but inappropriately managed cases will also be compared between people living at home and in care homes.

Missing data:

Our primary research objective was to measure the prevalence of a range of vision problems in a generic sample of people with dementia aged 60 to 89 years. The study is adequately powered to achieve this objective. The use of two groups of subjects is mainly to allow us to identify any differences in the level of undetected or inappropriately managed visual impairment between the two groups. This will inform Stage 2 of our study, in which we will investigate the reasons for any undetected or inappropriately managed visual impairment.

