Our sample size of 385 subjects in each group is based on an estimated prevalence of 50% with 5% precision and 95% confidence. This figure of 50% was the highest prevalence quoted in the literature for one of our target conditions. If the prevalence of a condition is either greater than or less than 50% then the study will require a sample size smaller than 385. We had anticipated that in a study of this nature there would be some missing data for each of the optometric tests as some of the participants/patients will be unable to perform them. There is no published data on the percentage of those with dementia who will be able to perform successfully individual elements of an eye examination. In the absence of published data we

took the view when writing our proposal that even if as few as 50% of subjects were able to complete a particular test with a prevalence of 50% (the worst case analysis) we would still have data from 385 subjects (50% of our total of 770), which is sufficient to generate a reliable estimate of the overall prevalence for the condition in a generic sample of patients with dementia.

Following the request for more detail on the impact of missing data we have consulted with a number of optometrists with extensive experience of eye examinations conducted on patients with dementia. Based on their responses we have quoted in Section 2 above (Testing people with dementia) estimates for the percentage of patients with dementia who are likely to be able to complete each test. The lowest percentage they estimate is 60%, compared with our worst case figure of 50% which was the figure used for our sample size calculation. Furthermore, these estimates suggest that, not only does our study have sufficient power to be able to generate a reliable generic figure for prevalence in dementia for each of our target conditions, but also that we should have sample sizes that are sufficiently large to allow statistical testing of differences in prevalence between our two groups (care home residents versus those living at home) for at least two thirds of the target conditions.

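### The care-home sample size and the home versus care-home test make no allowance for several residents coming from the same home

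*Protocol*

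**What the plan says.** Under Sampling, the protocol plans two groups "aged 60-89 years with 385 people in each group", one living at home and one in care homes, and explains that "The sample size has been calculated to allow detection of a prevalence of 50% with 5% precision and 95% confidence". The Missing data part of Data analysis repeats this basis and adds: "If the prevalence of a condition is either greater than or less than 50% then the study will require a sample size smaller than 385".

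Sampling also lists the recruitment routes. Both groups may come through memory clinics, old age psychiatry clinics and general practices, and a domiciliary eye-care provider is a further source for both. In addition, "Group 2 subjects will be recruited through direct contact with care homes". One large care provider has offered support, and "we will also recruit through other care providers to reduce the risk of selection bias". A further source is named: "DeNDRoN is launching the ENRICH research ready-care home network this year".

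For the analysis, Data analysis (Stage 1) fixes the comparison: "Prevalence levels between people living at home and people living in care homes will be compared using tests for two independent proportions". The proportions undetected and the proportions inappropriately managed are to be compared between the same groups. Prevalences will carry 95% confidence intervals; the formula is not named.

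Nothing in the protocol mentions clustering, an ICC, a design effect, the number of homes or a limit on residents per home.

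**The concern.** Residents of one home may resemble each other in whether a vision problem is present, known or properly managed. If they do, 385 residents carry less information than 385 unrelated people. A sample size and a test built on independence then understate the standard error for Group 2.

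The comparison is exposed because each care home lies wholly in one group, so variation between homes does not cancel in the contrast. The protocol says that the two groups exist mainly to show differences in undetected or inappropriately managed impairment, and home-level practice could plausibly matter most there. At stake are the stated precision of the care-home prevalence, the error rate of the between-group tests, and the claim under Missing data that samples will be large enough to test group differences for at least two thirds of the target conditions.

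**Working it through.** **Inputs from the protocol.** n = 385 per group (770 in total), prevalence p = 0.50, half-width 0.05, 95% confidence.

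**Assumed inputs.** Residents analysed per home (m) and ICC. The protocol gives neither, so a range is shown.

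**Step 1: reproduce the plan's figure.** n = 1.96² × 0.25 / 0.05² = 384.15 (with the unrounded normal quantile), which rounds up to 385. The match is exact with no design effect. At 385 independent people the half-width is 1.96 × √(0.25/385) = 4.99 points, so there is practically no slack.

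**Step 2: allow for homes.**
- Design effect: DE = 1 + (m − 1) × ICC.
- Half-width for Group 2: 1.96 × √(0.25 × DE / 385).
- True coverage of an interval that ignores clustering: 2Φ(1.96/√DE) − 1.
- True error of the nominal 5% test, with clustering in Group 2 only and equal group sizes: 2 × [1 − Φ(1.96/√((1 + DE)/2))].

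Worked case, m = 10 and ICC = 0.05: DE = 1 + 9 × 0.05 = 1.45; effective n = 385/1.45 = 266; half-width = 1.96 × √(0.25 × 1.45/385) = 6.0 points; test error = 2 × [1 − Φ(1.96/√1.225)] = 7.7%.

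| m | ICC | DE | Effective n of 385 | Half-width (points) | Coverage of unadjusted 95% CI | Test error |
|---|---|---|---|---|---|---|
| 1 | any | 1.00 | 385 | 5.0 | 95.0% | 5.0% |
| 2 | 0.01 | 1.01 | 381 | 5.0 | 94.9% | 5.1% |
| 5 | 0.02 | 1.08 | 356 | 5.2 | 94.1% | 5.5% |
| 10 | 0.05 | 1.45 | 266 | 6.0 | 89.6% | 7.7% |
| 15 | 0.10 | 2.40 | 160 | 7.7 | 79.4% | 13.3% |

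**Step 3: simulation check.** Beta-binomial data, 40,000 runs per case. For m = 10 and ICC 0.05, test error was 7.3% and coverage 89.1% at p = 0.5, and 7.8% and 89.9% at p = 0.2. For m = 5 and ICC 0.02, test error was 5.2% at p = 0.5 and 5.7% at p = 0.2. The results at p = 0.5 lie slightly below the formula; with practically no clustering, the test there ran at 4.7%.

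**Step 4: the pooled estimate.** With half the people in each group, half-width = 1.96 × √(0.25 × ((1 + DE)/2) / N).
- N = 770: 3.5 points with independence and 3.9 with DE = 1.45. For m from 5 to 20 and ICC from 0.01 to 0.10 it runs from 3.6 to 4.9, always inside 5.
- N = 385, the protocol's 50%-completion case, assuming half the completers from each group: 5.0 points with independence and 5.5 with DE = 1.45, and 5.0 to 7.0 over the same range. Here m counts completers per home, so non-completion also shrinks the clusters and favours the lower end.

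**The case against.** Several objections have force.

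- **Partial clustering.** A reader might infer that Group 2 is recruited home by home. Sampling does not say so: clinics, general practices and a domiciliary provider also supply Group 2, and direct contact with homes is an additional route. This limits the size. It does not remove the problem, since three of the named routes run through homes, providers or a care-home network.
- **Mechanism.** A reader might also infer that residents of a home share an eye-care provider, a case mix or an examiner. The protocol does not say this. Correlation within a home is plausible but assumed.
- **Pooled precision.** It is tempting to say that the overall prevalence, which the protocol calls its primary objective, also misses its precision. Step 4 shows otherwise at full completion. An unadjusted pooled interval would still be somewhat too narrow.
- **Lower prevalence.** The 6.0 points apply at 50%. At the 3.5% quoted in Background for vision loss from macular degeneration, the Group 2 half-width is 1.96 × √(0.035 × 0.965 × 1.45/385) = 2.2 points.
- **Smaller clusters for undetected cases.** If the denominator is impaired people only, 10 residents at an assumed 30% prevalence leave about 3 per home. With ICC 0.05, DE = 1.10 and test error is 5.6%. A higher ICC for this outcome could offset that, but none is given.
- **Confidence intervals and data forms.** The interval formula is not named, and a separate analysis plan could use cluster-robust intervals. That the intervals assume independence is only an inference from the 385 and the named test. The data forms are not shown, so a missing home identifier is not established either.

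What remains is what the protocol itself fixes: the 385 and the test. The description of recruitment as random, under Setting/ context, does not restore independence, because people are drawn within sites.

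**Conclusion.** The concern holds conditionally. The 385 contains no design effect and the named test assumes independence, while part of Group 2 comes through care homes. If more than one resident per home is analysed and the ICC is positive, the 5-point precision for Group 2 at 50% prevalence is not met and the between-group test exceeds 5% error. The direction is firm; the size is not known. It runs from negligible (2 per home, ICC 0.01: 5.0 points, 5.1% error) to material (15 per home, ICC 0.10: 7.7 points, 13% error). All of these values of m and ICC are assumptions, and they treat the whole of Group 2 as clustered. The statement that any prevalence other than 50% needs fewer than 385 is likewise safe only for independent participants. The pooled estimate is at risk of exceeding 5 points only in the 50%-completion case.

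**What to change.** - Record a care-home identifier for every Group 2 participant at examination.
- Compute Group 2 and pooled intervals with care home as the cluster, treating people living at home as clusters of one.
- Replace the two-independent-proportions test with a cluster-robust or GEE logistic comparison, also for undetected and inappropriately managed cases.
- State the expected number of homes and residents per home, and restate Group 2 precision with an assumed design effect and a range. Qualify the remark about needing fewer than 385.

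The cost is one data field and different analysis code. No extra participants are needed if precision is restated rather than preserved. Holding 5 points in Group 2 would instead take 384.15 × 1.45, or 558 people, in the case of 10 per home and ICC 0.05. The downside is somewhat wider intervals. The identifier should be in place before data collection, because it is harder to recover afterwards.

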- Where an LPA enables a consultee to consent on behalf of a potential participant, the consultee will be given an information sheet with the same information as a patient able to consent for themselves would have received, and be asked to sign a "Consultee Declaration Form" confirming that they
 - have read the information sheet giving details of the study
 - have had the opportunity to ask questions and understand what is involved
 have given their opinion whether he/she would not object to taking part in the
 - study
 - understand that participation is voluntary and that they can request that the patient is withdrawn from the study at any time without giving any reason and without their medical care or legal rights being affected
 - understand that relevant sections of medical notes may be looked at by the research team and information taken from them for use in this research, or in the monitoring of the research by clinical governance staff
 - understand that information will be held by the research co-ordinators
 - understand that records will be confidential and will be stored securely on systems within the NHS and University systems
 - understand that the GP of the person participating in the study will be informed of their participation in this study; and that the consultee agrees that data relating to the party participating in the study can be used in similar studies.
- It is recognised that patients with dementia often fluctuate in terms of their cognitive function and capacity; research staff will be alert to any signs of distress or unwillingness to continue in the study, formally expressed or otherwise. In these

cases the assessment procedure will be discontinued and the dementia patient will be withdrawn from the study.

In Stage 2 a total of 12 focus groups will be held, comprising three groups in each of the four centres (see Setting and Context) and three groups will focus separately on eye care professionals (community and hospital optometrists, ophthalmologists, dispensing opticians); professional carers (care home staff, day care staff, community support workers) and family carers. This reflects the recommendation that a minimum of three focus groups is conducted within any population in a study (27).

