During the examination of study patients the over-riding principle is that the optometrist should adopt a flexible approach throughout. The examination will be performed according to the cognitive and physical abilities of the patient, with the emphasis on objective assessments and omitting tests (both objective and subjective) as required. This approach is consistent with current College of Optometrists professional guidance on examining patients with dementia. When patients are to be examined in care homes, or in their own homes, appropriate advance warning of the optometrist's visit will be given to patients and carers.

On arrival at the care home/private home the optometrist will introduce themselves to the patient again, explaining again who they are and why they are there. The optometrist will then set up her/his equipment in the room allocated for the eye test (care home) or in the most appropriate available room if the test is to be carried out in the patient's own home. Where

there is a choice of room for the eye test, the ability to achieve dim illumination will be a major factor in the final selection.

Prior to commencing the eye test, participants will be asked if there are any tasks that they find particularly difficult. Where a participant is unable to respond appropriately advice will be taken from carers and/or care home staff as to the cognitive and other abilities of the patient.

The tests will normally be conducted in the following order, though flexibility is the watchword here and the order of tests can be adapted as required to suit the individual patient.

1. History and symptoms will be obtained from the carer and/or from the patient. When examined in a care home the optometrist will request access to the patient's care record (or ask staff to provide information from the record), from which information relating to general and ocular health can be obtained. Also, where necessary, input will be sought from carer(s) or care home staff regarding the patient's history and symptoms.

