Wherever possible, this retinoscopy result will be modified subjectively with the patient reading letters or symbols presented on the test chart through different lenses selected by the optometrist in order to refine the retinoscopy result. The patient's Visual Acuity with the final spectacle prescription found by retinoscopy or subjective examination will be recorded. It is estimated that retinoscopy will be possible on 70% of our patients, with subjective refinement possible in most of these (50% of the total sample). These results will contribute to the identification of uncorrected refractive error and visual impairment.

7. Posterior eye examination: At this stage in the test the patient's pupils will normally be dilated using tropicamide eye drops to facilitate the examination of the eye's structures behind the iris, notably the lens, the retina and other back of the eye structures. Prior to pupillary dilation, the likelihood of the pupil dilation provoking an acute angle closure glaucoma (ACG) attack will be assessed using the pen light test for anterior chamber depth estimation (Elliott 2007). The risk of provoking an acute ACG attack with tropicamide is very low (Pandit and Taylor 2000, report zero cases of ACG in almost 4000 dilations). However, patients judged at risk of an ACG attack will not be dilated and will be examined through undilated pupils.

The tropicamide drops take approximately 15 - 20 minutes to produce a sufficiently dilated pupil. During this time the patient can have a break, if required, the examiner can complete the MMSE if necessary, the strength of any current glasses can be measured using a focimeter, and the external eyes can be examined using the ophthalmoscope. Once the pupils are fully dilated the examination of each eye follows using a direct hand held ophthalmoscope. The patient needs only to keep their eyes open and, if possible, to follow instructions as to where to direct their gaze. It is estimated that direct ophthalmoscopy will be possible on 85% of our patients and the results will contribute to the identification of cataract, AMD, diabetic retinopathy and glaucoma suspects.

As a further check on the possibility of a dilation-induced acute ACG attack, post-dilation IOPs will be measured using the iCare tonometer. A significant increase in IOP could be an indicator of a pending ACG attack and if this is suspected the optometrist will remain for a further hour and continue to monitor the patient.

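### The home versus care-home comparison is planned as a crude test that ignores age mix, recruitment route and clustering within homes; an adjusted, cluster-robust difference should stand beside it

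*Protocol*

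**What the plan says.** Protocol, Data analysis, Stage 1: "Prevalence levels between people living at home and people living in care homes will be compared using tests for two independent proportions". The next sentence reads: "Proportions of both previously undetected cases and detected but inappropriately managed cases will also be compared between people living at home and in care homes". Neither names a covariate, a stratification, a standardisation or an allowance for clustering.

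Under Missing data, overall prevalence in a generic dementia sample is the primary objective. On impaired vision that is missed or badly handled, the same section says: "The use of two groups of subjects is mainly to allow us to identify any differences in the level of undetected or inappropriately managed". That result is to inform Stage 2, where reasons are investigated.

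Sampling shares some recruitment routes between the groups (NHS clinics, general practices). It adds Alzheimer's Society groups for people at home and direct contact with homes for care-home residents. A domiciliary eye-care provider may supply both groups, but especially people at home.

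Data collection, step 1, for everyone: "History and symptoms will be obtained from the carer and/or from the patient". For care homes it adds: "When examined in a care home the optometrist will request access to the patient's care record". Step 7 mentions cognition only as an option while the drops take effect: "the examiner can complete the MMSE if necessary".

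**The concern.** Two groups assembled in different ways can differ in prevalence, and in how much impairment is already known, for reasons unrelated to where people live. Age is the clearest case. The protocol admits ages 60 to 89, its Background shows a steep age gradient for cataract, and nothing in the design matches or balances age between groups. Recruitment route is another. Clients of an eye-care provider have, by the nature of that route, had contact with eye care, and the route is weighted to the home group.

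The named test also treats every participant as independent. Residents of one home plausibly share eye-care arrangements, so detection and management may be correlated within homes. The crude standard error would then be too small.

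At stake is the reading of the contrast for which the two groups were set up. A difference produced by age mix or recruitment could steer Stage 2, and the recommendations that follow, towards explaining a setting difference that is not there.

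**Working it through.** **Inputs from the protocol.** 385 per group, 50% prevalence, 5% precision, 95% confidence (Sampling; Missing data). Cataract visual impairment 16% at 65-69 and 71% at 85 and over (Background). Ophthalmoscopy, which contributes to identifying cataract, expected to be possible in 85% (Data collection, step 7). Lowest completion figure cited under Missing data: 60%.

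**Assumed, because the protocol gives no figure.** Two-sided 5% level and 80% power for the between-group test; the age mix of each group; the capture rates used in step 4.

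**1. The plan's own figure.** n = 1.96² × 0.5 × 0.5 / 0.05² = 384.15, rounded up to 385. It reproduces. It is a precision calculation for one proportion and does not size a comparison of two.

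**2. Difference detectable between groups near 50%.** d ≈ (1.96 + 0.84) × √(2 × 0.25 / n).
- n = 385: 2.80 × √(0.5/385) = 10.1 points.
- n = 327 (85% of 385): about 10.9 points.
- n = 231 (60% of 385): about 13 points.

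**3. Difference from age mix alone, with no effect of setting.** Let a be the share aged 85 and over, with everyone younger given the 65-69 rate. Prevalence = 0.16(1 − a) + 0.71a, so a gap s in that share gives a difference of 0.55 × s. With a = 30% at home (prevalence 32.5%):

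| Extra share aged 85+ in care homes | Care-home prevalence | Spurious difference | Crude test rejects, 385 per group |
|---|---|---|---|
| 10 points | 38.0% | 5.5 points | 36% |
| 20 points | 43.5% | 11.0 points | 88% |
| 30 points | 49.0% | 16.5 points | 99.7% |

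Giving everyone under 85 the 65-69 rate exaggerates the step. If they instead had the midpoint rate, (16 + 71)/2 = 43.5%, the step would be 71 − 43.5 = 27.5 points. The three differences would then halve to about 2.8, 5.5 and 8.3 points.

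**4. Secondary point: unequal capture of prior detection.** If a true share u is undetected in both groups and the history captures a fraction c of earlier detections, the apparent undetected share is u + (1 − u)(1 − c). Take u = 35%, c = 95% in care homes and 193 cases per group (about half of 385). Care homes then show 0.35 + 0.65 × 0.05 = 38.3%. For c = 85%, 80% or 70% at home, the apparent share there is 44.8%, 48.0% or 54.5%. The differences are 6.5, 9.8 and 16.3 points, and the test rejects 25%, 49% and 90% of the time. Every capture rate is an assumption; this shows sensitivity and does not estimate a bias.

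**5. Clustering.** With m residents per home and intra-home correlation ρ, the variance of the care-home proportion is multiplied by about 1 + (m − 1)ρ. The protocol gives neither m nor ρ, so the inflation is not sized here.

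**The case against.** The strongest reply is that the protocol makes no causal claim. It says the groups are there to identify differences and that Stage 2 will look for reasons. The contrast is not itself one of the four objectives. For describing unmet need by setting, crude proportions are a legitimate target, and an adjusted difference answers another question. This stands. A reader might infer that the crude test is invalid, or that the plan will attribute a difference to setting or eye care; the text supports neither. It is a reason to keep the crude figure, and it leaves the unmodelled clustering and the missing adjusted figure untouched.

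A second reply is that adjustment is commonly left to a statistical analysis plan. That would answer mere silence, but for prevalence the protocol names an unadjusted test. For the undetected and mismanaged proportions no test is named, so there the criticism is only that no adjustment is mentioned.

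Third, a reader might infer that prior detection is taken from records in care homes and from recall at home. The protocol does not say so. It neither defines the term nor names its source. Carer or patient report is common to both groups, and the consultee declaration allows for medical notes: "understand that relevant sections of medical notes may be looked at by the research team". What stands is that the definition is missing and that the one history step described has an extra source in care homes only.

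Fourth, the protocol does not say that care-home residents are older or more severely affected, does not mention sex as a collected variable, and makes the MMSE optional. A reader should not infer that all three covariates are at hand. The cataract figures come from a study of elderly acute geriatric admissions and concern prevalence, not the share undetected. They show how strongly age can act and do not estimate the bias in the undetected comparison.

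**Conclusion.** The concern holds in a limited form. As written, the between-group prevalence comparison is crude and assumes independence, and no adjustment is given for the comparison that mainly justifies two groups. Under the assumed age mixes, age alone could produce a cataract difference of 5.5 to 16.5 points, or about half that with a milder age gradient. The difference detectable with 80% power is about 10 to 11 points at 327 to 385 per group. Confounding of the same order as the detectable effect is therefore possible, though the protocol does not let its actual size be known.

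The overall prevalence estimates, which are the primary objective, do not depend on this between-group test. The missing definition of prior detection is a secondary point: unequal ascertainment is a risk the text leaves open, not something it establishes.

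**What to change.** 1. Keep the crude home versus care-home differences with confidence intervals and label them descriptive.
2. Beside them, prespecify a standardised risk difference from a logistic model (predicted risks averaged over the combined sample), adjusted for age, centre and recruitment route, and for sex where recorded, with standard errors clustered by care home. Some routes are open to one group only, so code route in categories that occur in both groups, and add a sensitivity analysis restricted to shared routes.
3. Use the MMSE only in a sensitivity adjustment. It is collected if necessary, and the Background reports cognitive improvement after cataract surgery, so the score may partly result from visual impairment.
4. Define 'previously undetected' and classify it from a source available in both groups, with an unknown category. If medical notes are to be that source, first check that participants' own consent covers it; the wording seen is in the consultee declaration.

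**Cost.** Age is already needed for eligibility; route and care-home identity must be recorded. The analysis takes a little more work and the intervals will be slightly wider. A common source for prior detection may add abstraction time and must be settled before data collection, because records not collected cannot be recovered by later adjustment.
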